2.6.7 Electrocardiogram

Standard 12-lead ECGs will be recorded at the visits and time points specified in Protocol Sections 1.2 and 1.3, and prior to any blood collections. For Day 1/Week 0, triplicate ECGs will be recorded within 5 minutes with at least 1 minute between 2 replicates prior to the study treatment administration.

Heart rate (in beats per minute), PR (in milliseconds), QRS (in milliseconds), QT-intervals (in milliseconds) and corrected QT-intervals (QTc) will be analyzed as observed parameter values and change from baseline (for HR, PR, QT, QTc). The corrected QT-interval (QTc) data will be analyzed using the Bazett (QTcB) and Fredericia (QTcF) methods.

For all parameters, the observed data and change from baseline will be summarized for each time point by age group cohorts and overall.

PCSA values will be summarized during the study (from first infusion start to last available observation) by age group cohorts and overall.

2.6.8 Doppler echocardiogram

A standard 2-dimensional and M-mode Echocardiogram (ECHO) with Doppler will be conducted at Screening, with the first infusion at 3.0 mg/kg or highest tolerated dose during Week 14 to Week 24 or whenever dose escalation is reached, and at Week 52. Examination will include but not be limited to: left ventricular cavity size, left ventricular mass, valve characterization, ejection fraction, ventricular wall thickness, regional wall motion, systolic and diastolic functions,

pericardium characterization and congenital abnormalities. Pulmonary artery pressure will be determined by Doppler ultrasound.

Shift tables will be created for valve characterization (including aortic regurgitation, mitral regurgitation, pulmonic regurgitation, tricuspid regurgitation). Summary of change from baseline in ejection fraction (%) and pulmonary artery systolic pressure will be provided. By-patient plots of left ventricular calculated ejection fraction (%) will be provided.

2.6.9 Liver ultrasound Doppler

Liver ultrasound Doppler will be performed at Screening and Week 52 to document hepatic blood flow characteristics, principally portal vein pressure and blood flow direction. The structures to be examined include hepatic portal vein, the main hepatic artery and the main hepatic vein.

Additional structures that may be examined include the network of intrahepatic portal veins, the main and intrahepatic arteries, the hepatic veins, the main and intrahepatic portal veins, the intrahepatic portion of the inferior vena cava, collateral venous pathways, and transjugular intrahepatic portosystemic shunts. Liver ultrasound Doppler will be performed using methods that are compatible with the standard institutional procedures of the investigational site.

Liver ultrasound Doppler data will be provided in listings.

2.6.10 Safety biomarkers

Biomarkers for monitoring the safety of olipudase alfa include, but are not limited to, high sensitivity C reactive protein (hsCRP), plasma ceramide, iron, ferritin, cardiac-specific troponin-1, calcitonin, interleukin (IL)-6 and IL-8. Samples will be collected at the visits specified in Protocol Sections 1.2 and 1.3.

Observed values, change from baseline and percent change from baseline will be summarized by age group cohorts and overall at each time point. Summary plots over time will also be presented for observed values as appropriate.

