	
Safety Analysis: Safety analyses will include a summary of treatment duration, the total number of infusions received, and the total amount of olipudase alfa received. Frequencies (number and percentage) of patients with one or more treatment-emergent adverse events (TEAEs) will be summarized according to the Medical Dictionary for Regulatory Activities (MedDRA) System Organ Class (SOC) and Preferred Term (PT) overall and by age group. All TEAEs, including those potentially related to study drug, those leading to treatment discontinuation and study discontinuation, infusion-associated reactions, serious adverse events (SAEs), and all AEs with fatal outcome (including fatal TEAEs) will be summarized overall and by age group. Other safety variables, including laboratory parameters and vital signs, will be summarized overall and by age group.
 
Pharmacokinetic Analysis: The pharmacokinetic analysis will be conducted on the pharmacokinetic analysis set. Plasma concentration-time data will be analyzed by non-compartmental methods, nonlinear mixed effects modeling, or by population-based analysis, based upon patient age and data suitability. Pharmacokinetic parameters will be calculated for each patient and summarized by age group, by dose (0.3, 1.0, 3.0 mg/kg), and by time point, and by manufacturing scale, including the week 52 visit.
 
Exploratory Efficacy Analysis: An assessment of exploratory efficacy will be conducted on the modified intent-to-treat analysis set. Efficacy summaries will include descriptive statistics of the observed value and/or change or percentage change (eg, spleen volume, liver volume, platelet count, etc.) from baseline to week 52 or week 64, as appropriate, including 95% confidence intervals. Categorical variables (eg, pulmonary imaging, chest X-ray) will be summarized using frequencies and percentages according to time points collected from screening or baseline to week 52 or week 64, as appropriate. Analysis will be performed overall and by manufacturing scale as appropriate.
 
Pharmacodynamic Analysis: The pharmacodynamic analysis will be conducted on the pharmacodynamic analysis set. Concentration of sphingomyelin and its metabolites will be summarized by dose and time point, and manufacturing scale as appropriate, using descriptive statistics.
 
Pharmacodynamic-Pharmacokinetic Analysis: Exploratory analyses may be performed to elucidate exposure-response relationships with biomarkers of safety and/or efficacy.

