The highest repeat-dose for this study, 3.0 mg/kg, is supported by nonclinical repeat-dose toxicology data and experience from the adult Phase 1b trial. This dose is 10 times less than the 30 mg/kg repeat dose NOAEL in ASMKO mice after a debulking regimen, and is 3.3 times less than the 10 mg/kg single dose, at which significant toxicity and deaths were observed in ASMKO mice without prior debulking. In the Phase 1b study, the safety and tolerability of within-patient dose escalation of olipudase alfa administered intravenously every two weeks for 26 weeks was studied. In this trial, 5 adult patients with NPD B were given ascending doses of olipudase alfa administered intravenously every two weeks, as tolerated, according to the following dose escalation schedule: 0.1, 0.3, 0.3, 0.6, 1.0, 2.0, and 3.0 mg/kg. The olipudase alfa dose was increased if the patient experienced no or only mild AEs at the lower dose. Patients were monitored in-hospital prior to and for at least 72 hours after olipudase alfa infusion during the dose escalation period, and during the first 2 doses at the maximum tolerable dose; thereafter patients were maintained at their maximum tolerable dose until the end of the 26-week treatment period and discharged after dosing and a 3-hour minimum observational period. Study assessments included continuous AE reporting and periodic evaluations of safety, pharmacokinetics, pharmacodynamics, and efficacy parameters.

All 5 patients completed the dose escalation regimen, receiving 3.0 mg/kg olipudase alfa, the highest dose allowed per protocol, and remained at that dose for the remainder of the study. Three patients completed the dose escalation regimen without a dose reduction or repeat. One patient had a dose reduction following a moderate IAR with the first olipudase alfa dose at 1.0 mg/kg;

subsequently, this patient continued dose escalation to 2.0 and 3.0 mg/kg olipudase alfa. One patient repeated the 2.0 mg/kg olipudase alfa dose following a moderate IAR and subsequently dose escalated to 3.0 mg/kg. Adverse events were mild or moderate with those considered related to olipudase alfa administration generally occurring between 12 and 48 hours post-dose. The most commonly reported of these events were headache, arthralgia, abdominal pain, and nausea. Plasma ceramide levels typically peaked 48 hours post-dose and attenuated with repeat dosing.

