#### **11.4.2.7 Safety biomarkers**

For safety biomarkers of ceramide, cardiac troponin I, hsCRP, calcitonin, iron, ferritin, IL-6 and IL-8 raw values and change from baseline will be summarized using descriptive statistics by age group cohort, time point, highest tolerated dose and overall time point.

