#### **11.4.4 Pharmacodynamic analyses**

Pharmacodynamic endpoints are defined in [Section 9.2.3](#).

Concentration-time data for sphingomyelin and metabolite levels (eg, ceramide, lyso-sphingomyelin) will be summarized using descriptive statistics. If appropriate, the following parameters will also be assessed:  $C_{max}$ ,  $T_{max}$ , and area under the effect-time curve. Individual and descriptive statistics will be presented.

Pharmacodynamic parameters will be summarized using descriptive statistics using the pharmacodynamics population. Change from baseline will be calculated and summarized.

Exploratory correlation analyses will be attempted to evaluate relationships between different pharmacodynamic markers and between sphingomyelin levels from different sources.

These analyses will be conducted by age cohort – in overall population as well as by manufacturing scale, as appropriate.

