2.9.2 Statistical analysis

Concentration-time data for sphingomyelin and metabolite levels (eg, ceramide, lyso-sphingomyelin and sphingosine-1-phosphate), observed, change from baseline and percent change from baseline, will be summarized by age group cohorts and overall. Summary plots over time will be provided.

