2.11.3 Windows for time points

Statistical analysis will be based on the nominal visit which should follow schedule defined in protocol Section 1.2. Visits will not be windowed for analysis purposes, except for unscheduled visits in some cases as described in [Section 2.11.4](#).

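### SAP summarises safety biomarkers and PD markers by visit but not by dose, without declaring it; escalation visits can then mix doses, and scheduled 24/48 h values at Weeks 20-24 come only from patients behind schedule

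*SAP*

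**What the plan says.** **SAP.** Section 2.6.10 (safety biomarkers) says: "Observed values, change from baseline and percent change from baseline will be summarized by age group cohorts and overall at each time point". Section 2.9.2 says that the PD concentrations, with their change and percent change from baseline, "will be summarized by age group cohorts and overall. Summary plots over time will be provided". Section 2.11.3 sets the time axis: "Statistical analysis will be based on the nominal visit". Section 2.11.4 keeps unscheduled values out of by-visit summaries. Section 1.5, which lists departures from the protocol's statistical section, does not mention dose.

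**Protocol.** The synopsis, on PD: "Concentration of sphingomyelin and its metabolites will be summarized by dose and time point". Section 11.4.2.7, on safety biomarkers: "descriptive statistics by age group cohort, time point, highest tolerated dose and overall time point". Section 11.4.4, on PD, names a different set of strata: "These analyses will be conducted by age cohort", then overall and by manufacturing scale, with no mention of dose. The protocol is therefore not uniform about PD.

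**Sampling schedule.** Under protocol 1.3, 1.4 and 10.3.2 to 10.3.5, post-infusion samples for these markers are taken at escalation visits, at the second infusion at the highest tolerated dose, and at quarterly visits. The 24 h sample applies to adolescents only. At other visits before Week 26, section 10.3.6 schedules pre-infusion samples only.

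**The concern.** These markers are sampled after infusion for a stated purpose. Protocol 6.4.1.1 reports dose-related rises in ceramide, hsCRP and other reactants at 24 to 48 hours in the single-dose adult study, and their attenuation under stepwise escalation. Section 6.4 reports that the ceramide peak shrank with repeat dosing. Section 10.6.1.3.2.3 ties IL-6 and IL-8 rises to the first administrations at particular dose levels. The protocol's own axes are thus dose level and infusion order.

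A nominal visit stands in for dose only while every patient is on schedule. Once patients diverge, an escalation-visit mean can average different doses. Because post-infusion sampling follows each patient's escalation rather than the calendar, the set of patients sampled at Weeks 20-24 also changes. A reader of the visit tables could take a change in dose mix, or in who was sampled, for a change in response.

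**Working it through.** **1. Dose by week, on schedule.** From protocol 8.3.2, with infusions every 2 weeks from Week 0:

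| Week | 0 | 2 | 4 | 6 | 8 | 10 | 12 | 14 | 16 | 18 |
|---|---|---|---|---|---|---|---|---|---|---|
| mg/kg | 0.03 | 0.1 | 0.3 | 0.3 | 0.6 | 0.6 | 1.0 | 2.0 | 3.0 | 3.0 (second) |

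Protocol 10.3.4 agrees: it places the first 1.0 mg/kg infusion at Week 12 where applicable.

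**2. Reproducing the planned sample counts.** The safety-biomarker rows of protocol Tables 4 to 6 give 43 samples (adolescent), 30 (child and 3 to <6 years) and 30 (up to 2 years). On schedule there are 5 quarterly visits including Day 1, 8 escalation or second-3.0 visits (Weeks 2, 4, 6, 8, 10, 14, 16, 18), 3 pre-infusion-only visits (Weeks 20, 22, 24) and Week 64.
- Adolescent (pre, 24 h, 48 h): 5×3 + 8×3 + 3×1 + 1 = 43.
- Child and 3 to <6 years (pre, 48 h): 5×2 + 8×2 + 3×1 + 1 = 30.
- Up to 2 years (pre, 48 h): the same sum, 30.

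All three match. Had on-schedule patients been meant to give post-infusion samples at Weeks 20-24, the first two counts would be 43 + 3×2 = 49 and 30 + 3×1 = 33. (The PD rows are less reliable: Table 5 states 43 and Table 6 states 29, against 30 counted for each. I rest on the safety-biomarker rows.)

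**3. Effect of delay**, counted in 2-week steps, for a patient who goes on to reach 3.0 mg/kg:

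| Steps behind | Second 3.0 mg/kg infusion | Post-infusion samples at Weeks 20-24 |
|---|---|---|
| 0 | Week 18 | none |
| 1 | Week 20 | Week 20 |
| 2 | Week 22 | Weeks 20, 22 |
| 3 | Week 24 | Weeks 20, 22, 24 |

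A delay can come from a related AE (8.3.4.1) or from a missed infusion for any reason (8.3.3).

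**4. How likely is any divergence?** The only rate in the documents is the adult Phase 1b study: "Three patients completed the dose escalation regimen without a dose reduction or repeat", out of 5, so 2 of 5 = 40% (exact 95% CI 5% to 85%). With 20 patients and a common, independent rate p, P(at least one off schedule) = 1 − (1 − p)^20:
- p = 0.05: 0.64
- p = 0.20: 0.99
- p = 0.40: above 0.999

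**5. Illustration.** Assume 20×0.40 = 8 of 20 patients each repeat one dose, 4 at 1.0 and 4 at 2.0 mg/kg (the two levels at which the adult events occurred).
- Week 14: 16 at 2.0, 4 at 1.0 mg/kg.
- Week 16: 12 at 3.0, 8 at 2.0 mg/kg.
- Weeks 0 to 12, and Week 18 onward: one dose per visit.
- Patients with post-infusion samples: 20 at Week 18, 8 at Week 20, 0 at Weeks 22 and 24, 20 at Week 26.

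**The case against.** **Against the departure.** A reader might infer that the protocol planned safety biomarkers by dose at the visit and that the SAP removed this. It did not. Section 11.4.2.7 asks for "by age group cohort, time point, highest tolerated dose and overall time point". Highest tolerated dose is one value per patient, so restoring it would not separate doses within a visit, and summarising by time point is itself the protocol's plan. For PD, only the synopsis names dose. This stands. What remains is that a by-dose PD summary and a highest-tolerated-dose summary were planned and are absent, without an entry in SAP 1.5. Parts of the SAP are redacted, but the sentences in 2.6.10 and 2.9.2 are complete.

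**Against the size.** A reader might infer that every visit mixes doses. Week 0 is always 0.03 mg/kg, and on-schedule patients share one dose throughout. The adult events do not support a shifted dose at Week 12, because both occurred at levels that fall at Week 12 or later here. That study also started at 0.1 mg/kg with a single 0.6 step, so its rate may not carry over. One 2-week delay affects post-infusion sampling at Week 20 only. This stands too.

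**Against the consequence.** SAP section 2 reports n with every continuous summary and supports tables with listings, so a fall from 20 to 8 would be visible. Observed values are reported beside changes from baseline, which is the protocol's own measure. The summaries are descriptive, escalation and stopping follow AEs and liver tests, and the SAP keeps dose for TEAEs (2.6.1.2) and PK (2.7.2). This limits the harm. But n alone shows neither which dose the values follow nor that the remaining patients are the delayed ones.

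**Conclusion.** The point holds in limited form. SAP 2.6.10 and 2.9.2 have no dose term, and SAP 1.5 does not declare the loss of the two planned summaries. Once any patient is off schedule, escalation-visit means can mix doses, chiefly at Weeks 14 and 16 if delays occur at 1.0 or 2.0 mg/kg. Scheduled 24/48 h values at Weeks 20-24 come only from patients at least one infusion behind. That follows from the schedule, and the reproduced counts of 43, 30 and 30 support it. Pre-infusion means are not affected by this sampling selection.

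The size depends on an unknown off-schedule rate. At 5%, one patient of 20 is expected, and a Week 20 post-infusion mean could rest on that patient; at the adult 40% it could rest on about 8. Weeks 22 and 24 matter only with two and three 2-week delays.

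Two stronger readings are not supported. The Week 20-24 patients cannot be described as those who failed to tolerate escalation, since infusions are also missed for other reasons. Nor do the documents show that the tables would display a false late surge: they give no marker values by delay status. No test or dosing decision rests on these tables. The loss is in how clearly the plan answers its own questions about dose relation and attenuation.

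**What to change.** In SAP 2.6.10 and 2.9.2:

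1. Keep the nominal-visit tables, and for post-infusion values at Weeks 14-24 show n and the dose mix.
2. Add pre-infusion, 24 h and 48 h summaries by administered dose, using the infusions scheduled at each level: first 0.03, first 0.1, first and second 0.3, first and second 0.6, first 1.0, first 2.0, first 3.0, and second at 3.0 mg/kg or highest tolerated dose. List extra repeats separately, because an additional cell such as a repeated 1.0 mg/kg would again hold only delayed patients.
3. For 24 h and 48 h values, also report the paired change from the same visit's pre-infusion value. This adds to the change from baseline and does not replace it.
4. Restore the highest-tolerated-dose summary of safety biomarkers, or declare its removal in SAP 1.5. Record there also how the synopsis and protocol 11.4.4 are reconciled on PD by dose.

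Confining post-infusion visit summaries to quarterly visits would be a poor alternative. It would drop time points that protocol 11.4.2.7 plans to summarise and, since IL-6 and IL-8 are not required at Weeks 26, 38 or 52 (protocol 1.3, footnote f), would leave only Day 1 and Week 12 for those two.

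Cost: SAP wording and a few descriptive tables, some with small cells. Administered dose and same-visit pre-infusion values are already collected.

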2.6.11 Immune response assessments

An immune reaction against an exogenously administered recombinant protein plays a critical role in the safety of such compounds. Therefore, safety assessments will also include blood samples for anti-olipudase alfa immunoglobulin G (IgG) antibodies and neutralizing antibody formation in patients testing positive for ADA when appropriate.

In the event that a patient experiences a moderate, severe, or recurrent IAR suggestive of hypersensitivity reactions, additional blood samples will be collected for the evaluation of:

- Circulating immune complex detection; and,
- Immunoglobulin E (IgE) ADA, serum tryptase, and complement activation.

Additionally, skin testing may be performed, as appropriate, in patients who experience an IAR that meets the following criteria:

- IAR is suggestive of IgE ADA – mediated hypersensitivity reaction, with persistent symptoms of bronchospasm, hypotension and/or urticaria requiring intervention,
- Or any other signs or symptoms at the discretion of the investigator or the sponsor.

For ADA summaries, the baseline is the last non-missing ADA assessment prior to the first IMP.

Data listings will be provided to display results of anti-olipudase IgG antibody, neutralizing antibody, anti-olipudase alfa IgE antibody, serum tryptase activity, complement activation, and skin testing performed. If IgG ADA titer value is reported as <xx, the numeric value will be imputed as xx, the minimum required dilution (MRD), and used for summary purposes. Listing will provide results as reported as well as results as imputed.

A patient with at least one anti-drug antibody (ADA) response available in the database is considered evaluable.

A patient whose ADA status is positive at baseline is considered to have pre-existing ADA.

A patient whose ADA status is positive anytime post-baseline and is negative or missing at baseline is considered to have treatment-induced ADA.

A patient whose ADA status is positive at baseline (pre-existing ADA) and the ADA titer level anytime post-baseline is significantly higher than that at baseline is considered to have treatment-boosted ADA. A difference in titer values between 2 samples representing greater than or equal to twice the dilution level is considered significant. In other words, if the post-baseline titer value divide by the baseline titer value is greater than or equal to 4, then the patient is considered to have treatment boosted ADA. For example, if baseline titer value is 50, the post-baseline titer value has to be ≥ 200 .

For patients with treatment-induced ADA, the following 3 ADA responses are defined:

Transient ADA response:

- Treatment-induced ADA detected only at one sampling time point post-baseline (excluding the last sampling time point).
- Treatment-induced ADA detected at two or more sampling time points post-baseline, where the first and last ADA-positive samples (irrespective of any negative samples in between) are separated by a period less than 16 weeks, and the subject's last sampling time point is ADA-negative.

Persistent ADA response:

- Treatment-induced ADA detected at two or more sampling time points post-baseline, where the first and last ADA-positive on-treatment sample (irrespective of any negative samples in between) are separated by at least 16 weeks.
- Treatment-induced ADA detected in the last two sampling time points, irrespective of the time period in between.

The following sub-classifications for persistent ADA response will be considered as well.

- Low response – if a patient's peak titer ≤ 400 and positive at final assessment. This represents the first titer that is greater than a 4-fold increase from the assay minimum required dilution (MRD). Titers within this range would be considered as Low response.
- Intermediate ADA response - if a patient had persistent ADA response but peak titer is >400 and positive at final assessment.
- Tolerized – if a patient had persistent ADA response, but negative at the final assessment.

Indeterminate ADA response:

- Only the last sampling time point is positive and all previous samples are negative.

Pre-existing ADA and ADA Incidence rate are defined as follows:

Pre-existing ADA = $100 * (\text{Number of patients pre-existing ADA at baseline}) / \text{number of evaluable patients}$.

ADA Incidence = $100 * (\text{treatment-boosted} + \text{treatment-induced ADA positive patients}) / \text{number of evaluable patients}$.

The following information will be provided by age group cohorts and overall:

- Number of ADA evaluable patients
- Number (%) of patients with ADA positive/negative at baseline
- Number (%) of patients that never develop ADA at any time (i.e, ADA always negative during baseline and post-baseline)
- Number (%) of patients with treatment-boosted ADA
- Number (%) of patients with treatment-induced ADA
- Treatment emergent ADA: Number (%) of patients with treatment-boosted/treatment-induced ADA
- Duration of ADA response: Number (%) of patients with transient/persistent/indeterminate ADA response (each category separately)
- Number (%) of patients within persistent ADA response sub-classifications: low response, intermediate response, tolerized (each category separately)
- Patients with treatment induced ADA will be further characterized
 - Peak ADA titer: Median and 25th/75th quantiles (min, max) of the ADA titer for peak ADA titer of treatment induced ADA positive patients
 - Last ADA titer (final assessment): Median and 25th/75th quantiles (min, max) of the ADA titer of treatment induced ADA positive patients
- Number (%) of patients with positive neutralizing antibody (NAb)

- NAb inhibition of catalytic activity
- NAb inhibition of cellular uptake

